### **8.6.1 Statistical Methods for Efficacy Analyses**

This section describes the statistical methods that address the primary and secondary objectives. [REDACTED]

#### **8.6.1.1 Progression-Free Survival (PFS)**

To address the primary PFS hypothesis, the Kaplan-Meier method will be used to estimate the PFS curve in each treatment group. The treatment difference in PFS will be assessed by the stratified log-rank test. A stratified Cox proportional hazard model with Efron's method of tie handling will be used to assess the magnitude of the treatment difference (i.e., hazard ratio) between the treatment groups. The hazard ratio and its 95% confidence interval from

the stratified Cox model with Efron's method of tie handling and with a single treatment covariate will be reported. The same stratification factors used for randomization (see Section 5.4) will be applied to both the stratified log-rank test and the stratified Cox model.

Since disease progression is assessed periodically, progressive disease (PD) can occur any time in the time interval between the last assessment where PD was not documented and the assessment when PD is documented. In the primary analysis, for the subjects who have PD, the true date of disease progression will be approximated by the date of the first assessment at which PD is documented based on RECIST 1.1 by independent central review, regardless of discontinuation of study drug. Death as a first event is always considered as a confirmed PD event.

In order to evaluate the robustness of the PFS endpoint, two sensitivity analyses will be performed, each with a different set of censoring rules. The first sensitivity analysis is the same as the primary analysis except that it censors at the last disease assessment without PD when PD or death is documented after more than one missed disease assessment. The second sensitivity analysis is the same as the primary analysis except that it considers discontinuation of treatment or initiation of new anticancer treatment, whichever occurs later, to be a PD event for subjects without documented PD or death. The censoring rules for primary and sensitivity analyses are summarized in [Table 11](#).

Table 11 Censoring Rules for Primary and Sensitivity Analyses of PFS

Situation	Primary Analysis	Sensitivity Analysis 1	Sensitivity Analysis 2
No PD and no death; new anticancer treatment is not initiated	Censored at last disease assessment	Censored at last disease assessment	Censored at last disease assessment if still on study therapy; progressed at treatment discontinuation otherwise
No PD and no death; new anticancer treatment is initiated	Censored at last disease assessment before new anticancer treatment	Censored at last disease assessment before new anticancer treatment	Progressed at date of new anticancer treatment
PD or death documented after $\leq 1$ missed disease assessment	Progressed at date of documented PD or death	Progressed at date of documented PD or death	Progressed at date of documented PD or death
PD or death documented after $\geq 2$ missed disease assessments	Progressed at date of documented PD or death	Censored at last disease assessment prior to the $\geq 2$ missed disease assessment	Progressed at date of documented PD or death

In case there is an imbalance between the treatment groups on disease assessment schedules or censoring patterns, the following two additional PFS sensitivity analyses may be performed: 1) a PFS analysis using time to scheduled tumor assessment visit from randomization as opposed to actual tumor assessment time; 2) Finkelstein's likelihood-based score test for interval-censored data [54] which modifies the Cox proportional hazard model for interval censored data, will be used as a supportive analysis for the PFS endpoint. The interval will be constructed so that the left endpoint is the date of the last disease assessment without documented PD and the right endpoint is the date of documented PD or death, whichever occurs earlier.

The proportional hazards assumption on PFS will be examined using both graphical and analytical methods if warranted. The log [-log] of the survival function versus time for PFS will be plotted for the comparison between pembrolizumab and the control group. If the curves are not parallel, indicating that hazards are not proportional, supportive analyses may be conducted to account for the possible non-proportional hazards effect associated with immunotherapies: for example, using Restricted Mean Survival Time (RMST) method [55], parametric method [56], comparison of PFS at fixed follow-up times (6 months; 1 year) etc. Further details of sensitivity analyses will be described in supplemental SAP.

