## 2.0 TRIAL DESIGN

### 2.1 Trial Design

**NOTE: As of Amendment 10, the epacadostat/placebo combination therapy is removed from both treatment groups. All subjects remaining in the trial continue on pembrolizumab alone in an open-label fashion. The Second Course retreatment phase is removed. The last trial visit is the Safety Follow-up Visit.**

This is a randomized, placebo-controlled, parallel-group, multi-site, double-blind trial of pembrolizumab and epacadostat in subjects with unresectable or metastatic melanoma to be conducted in conformance with Good Clinical Practices. This Phase 3 study will be conducted in subjects with unresectable or metastatic melanoma. Subjects will be stratified by programmed cell death ligand 1 (PD-L1) expression (positive versus negative/indeterminate) and BRAF mutation status (BRAF mutant and received prior BRAF directed treatment, BRAF mutant with no prior BRAF directed treatment and BRAF wild type) and then be randomized 1:1 (active:placebo) to Treatment A (pembrolizumab + epacadostat) or Treatment B (pembrolizumab + placebo). No treatment crossover is planned.

The treatment period with the combination therapy will continue every 21 days for up to 35 cycles (approximately 2 years) as long as subjects are receiving benefit from treatment and have not had disease progression or met any criteria for study withdrawal.

Specific procedures to be performed during the trial, as well as their prescribed times and associated visit windows, are outlined in the Trial Flow Chart - Section 6.0. Details of each procedure are provided in Section 7.0 – Trial Procedures.

This trial will use an adaptive design based on pre-specified criteria, using an independent, external Data Monitoring Committee (DMC) to monitor safety and efficacy. There will be 2 interim analyses, as stated in Section 8.7.

Results of the interim analysis will be reviewed by the external DMC, which will make recommendations to continue, modify or end the trial according to the plan described in detail in Section 8.0 - Statistical Analysis Plan.

An interim review of the data indicated no benefit of epacadostat over placebo when combined with pembrolizumab. The external DMC recommended that all subjects be unblinded and all epacadostat and placebo administration stop. The study will remain open so that subjects still on study will have continued access to pembrolizumab.

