##### **5.8.1 Discontinuation of Treatment**

Discontinuation of treatment does not represent withdrawal from the trial.

As certain data on clinical events beyond treatment discontinuation may be important to the study, they must be collected through the subject's last scheduled follow-up, even if the subject has discontinued treatment. Therefore, all subjects who discontinue trial treatment prior to completion of the treatment period will still continue to participate in the trial as specified in Section 6.0 - Trial Flow Chart and Section 7.1.8.5 – Post-Trial.

Subjects may discontinue treatment at any time for any reason or be dropped from treatment at the discretion of the investigator should any untoward effect occur. In addition, a subject may be discontinued from treatment by the investigator or MSD if treatment is inappropriate, the trial plan is violated, or for administrative and/or other safety reasons. Specific details regarding procedures to be performed at treatment discontinuation are provided in Section 7.1.7 – Other Procedures.

A subject must be discontinued from treatment but continue to be monitored in the trial for any of the following reasons:

- The subject or subject's legally acceptable representative requests to discontinue treatment.
- The subject has a medical condition or personal circumstance which, in the opinion of the investigator and/or MSD, placed the subject at unnecessary risk from continued administration of study drug/vaccine.
- The subject has a confirmed positive serum pregnancy test.
- Confirmed radiographic disease progression outlined in Section 7.1.5 (exception if MSD approves treatment continuation).
- Unacceptable adverse experiences as described in Section 7.2.

- Any progression or recurrence of any malignancy, or any occurrence of another malignancy that requires active treatment. Note: **For France only**, a subject experiencing this condition must be discontinued from the trial.
- Intercurrent illness other than another malignancy as noted above that prevents further administration of treatment.
- Recurrent Grade 2 pneumonitis.
- Any toxicity listed in Section 5.2.1.2, [Table 2](#), with a requirement to permanently discontinue.
- Non-compliance with trial treatment or procedure requirements.
- Investigator's decision to discontinue treatment.
- Administrative reasons.
- Completed 35 treatments with pembrolizumab.

Note: 35 cycles (approximately. 2 years) are calculated from the first dose.

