- Discontinuation of treatment may be considered for subjects who have attained a confirmed CR and have been treated for at least 8 cycles (at least 24 weeks) and had at least 2 cycles of the combination (at least 2 doses of pembrolizumab) beyond the date when the initial CR was declared.

The End of Treatment and Follow-up visit procedures are listed in Sections 7.1.8.4 and the Trial Flow Chart - Section 6.0.

For subjects who are discontinued from treatment but continue to be monitored in the trial, see Section 6.0 – Trial Flow Chart, and Section 7.1.8.4 – Post-Trial for those procedures to be completed at each specified visit.

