### **8.7.1 Efficacy Interim Analyses**

Three analyses (two interim and one final) are planned in this trial. [Table 14](#) provides the summary of the strategy and timing of the interim and final analyses. Accrual is expected to be completed prior to the first interim analysis. The final analysis of PFS will be performed at interim analysis 2 (IA2) scheduled to be performed at about 420 PFS events (about 24 months following the start of enrollment). The final analysis of OS will be performed at about 293 OS events (about 45 months following the start of enrollment).

Table 14 Summary of Interim Analysis Strategy

Analysis	Key endpoints	Targeted number of events at the time of analysis	Expected approximate timing of analysis (from study start)	Primary purpose of analysis
IA 1	PFS OS	Approximately 331 total PFS events. About 100 OS events are expected at IA1.	About 12 months	First interim analysis of PFS: demonstrate superiority of combination in PFS. First interim analysis of OS; Demonstrate superiority of combination in OS.
IA 2	PFS OS	Approximately 420 total PFS events. This is the final PFS analysis. About 200 OS events are expected at IA2.	About 24 months	Final analysis of PFS: demonstrate superiority of combination in PFS. Second interim look at OS; Demonstrate superiority of combination in OS.
Final	OS	Approximately 293 total OS events. This is the final OS analysis.	About 45 months	Final OS analysis: Demonstrate superiority of combination in OS.

Table 15 provides the details of the interim efficacy monitoring boundaries for PFS and OS.

Table 15 Decision Guidance at IA1 and IA2 PFS Analyses and Each OS Analysis under a Hypothetical Timings of Interim Analyses and Initially Assigned Alpha

Analysis	Targeted number of PFS events	One-sided PFS Efficacy boundary p-value	PFS observed hazard ratio	OS events	One-sided OS efficacy boundary p-value	OS observed hazard ratio
IA 1	~331	< 0.0053	< ~0.75	~100	< 0.0001	< ~0.46
IA 2 (Final PFS analysis)	~420	< 0.0108	< ~0.80	~200	< 0.0029	< ~0.68
Final OS Analysis				Targeted for ~293	< 0.0115	< ~0.77

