**ORR analysis:** Should the definitive OS analysis be statistically significant, the definitive ORR analysis will be performed using the data available at IA2. Assuming the available alpha for the ORR comparison is 2.5% and an ORR of 35% for the pembrolizumab + placebo regimen, the study has ~97% power to detect an ORR rate for the combination regimen of 50%.

The above calculations are based on the following assumptions (in addition to the interim analysis plan in Section 8.7): 1) OS for the pembrolizumab + placebo regimen follows a distribution with a “cure” rate of 35%, with survival for the remaining 65% of patients following an exponential distribution with a median of 14 months; 2) PFS follows a distribution with a “cure” rate of 30%, with PFS for the remaining 70% of patients following an exponential distribution with a median of 4.75 months in the pembrolizumab + placebo regimen; 3) the hazard ratio for OS between the pembrolizumab + epacadostat combination and pembrolizumab + placebo is 0.7; 4) hazard ratio for PFS between the pembrolizumab + epacadostat combination and pembrolizumab + placebo is 0.65 and 5) an enrollment period of approximately 12 months. The sample size and power calculation were performed in the software R package gsDesign (see R code, Section 12.10).

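### PFS Sensitivity Analysis 2, as written, scores subjects who complete 35 pembrolizumab treatments or stop in confirmed CR as progressed; completion alone shifts the month-24 HR by 0.01 or less on average

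*Combined protocol and SAP*

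**What the plan says.** Section 8.6.1.1 plans two sensitivity analyses of PFS with different censoring rules. The narrative says of the second that "it considers discontinuation of treatment or initiation of new anticancer treatment, whichever occurs later, to be a PD event for subjects without documented PD" (the sentence goes on to add death). For subjects without PD, death or new anticancer treatment, Table 11 puts it this way: "Censored at last disease assessment if still on study therapy; progressed at treatment discontinuation otherwise". Neither place makes an exception by reason for stopping. For the same subjects the primary analysis and Sensitivity Analysis 1 censor at the last disease assessment.

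Section 5.8.1 defines what counts as discontinuing treatment. Its list of reasons includes "Completed 35 treatments with pembrolizumab". It also says: "Discontinuation of treatment may be considered for subjects who have attained a confirmed CR and have been treated for at least 8 cycles".

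Section 8.6.1.1 ends: "Further details of sensitivity analyses will be described in supplemental SAP". That document is not part of the material.

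**The concern.** Counting a treatment stop as an event is a sensible stress test when the stop may hide a failure, such as unrecorded clinical deterioration. Finishing the planned course without progression, or stopping in confirmed CR, is the opposite: one is planned and the other favourable. Under the rule as written both become PD events on the stop date, and only subjects still on therapy are spared.

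What is at stake is how this one robustness result is read. The misclassified subjects are the long-term progression-free ones, so the arm with more of them collects more artificial events. The sensitivity HR could then differ from the primary HR for reasons that have nothing to do with progression.

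**Working it through.** **1. Treatment of a subject with no PD, death or new anticancer treatment**

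| Reason off treatment | Primary | Sensitivity 1 | Sensitivity 2 as written |
|---|---|---|---|
| Still on therapy | censored | censored | censored |
| Stopped for toxicity or another reason | censored | censored | PD event at stop |
| Completed 35 treatments (5.8.1) | censored | censored | PD event at stop |
| Stopped in confirmed CR (5.8.1) | censored | censored | PD event at stop |

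A subject whose PD or death is documented later keeps that date, so the problem concerns only subjects event-free at the cut.

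**2. The plan's own figures.** Section 12.10 gives 331 and 420 events, HR 0.65, one-sided alpha 0.0125 and exponential spending with ν = 0.75. Spend at IA1 is 0.0125^((331/420)^−0.75) = 0.0053. The nominal p at IA2 is 0.0108. Boundary HRs, exp(−2z/√events), are 0.755 and 0.799, and power is 98.4%. These agree with Table 15 and Section 8.9.1, so the design inputs are usable.

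**3. Inputs for completion**
- Control PFS (8.9.1): S(t) = 0.30 + 0.70·exp(−ln2·t/4.75).
- Effect: Section 8.9.1 says only that the "hazard ratio for PFS between the pembrolizumab + epacadostat combination and pembrolizumab + placebo is 0.65". I read it as whole-arm, S^0.65, or as acting on the non-cured only, 0.30 + 0.70·exp(−0.65·ln2·t/4.75). I add a no-effect case because Section 2.1 reports: "An interim review of the data indicated no benefit of epacadostat over placebo when combined with pembrolizumab".
- N = 700, 1:1, 12-month enrollment (8.9.1). Uniform accrual is my assumption.
- Dose 35 falls at 34 × 21 / 30.4375 = 23.46 months.
- IA2, the final PFS analysis, is expected about month 24 (8.7.1).

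**4. Completers at month 24.** The maximum per arm, if every progression-free subject stays on drug, is 350 × (24 − 23.46)/12 × S(23.46).

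| Reading | S(23.46), control / combination | Completers |
|---|---|---|
| Whole-arm 0.65 | 0.323 / 0.480 | 5.1 + 7.6 ≈ 13 |
| Non-cured only | 0.323 / 0.376 | 5.1 + 5.9 ≈ 11 |
| No effect | 0.323 / 0.323 | 5.1 + 5.1 ≈ 10 |

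Using the −3-day dosing window at dose 35 raises 13 to about 15. Dating completion at the end of cycle 35 (35 × 21 / 30.4375 = 24.15 months) gives none.

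**5. HR shift from completion at month 24.** I simulated this model with an unstratified Cox fit and Efron ties. The two effect readings used 3,000 trials of 700.
- Whole-arm: mean shift +0.008 with completion at week 102, +0.0096 with the −3-day window, 0 at week 105.
- Non-cured: +0.004, +0.005 and 0.
- No effect (500 trials): 1.005 under both rules.

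These are averages. In the whole-arm, week-102 case about 25% of single trials shift by more than 0.01 (97.5th percentile 0.016).

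**6. Event-driven cut.** IA2 is triggered by events. With no effect, 420 events require 490 × (1 − x) = 420, so x = 0.143, the mean of exp(−ln2·f/4.75) over follow-up times f between T − 12 and T. This solves to T = 20.2 months, before anyone reaches dose 35. The non-cured reading gives month 23.6 and a shift of about 0.001. The whole-arm reading gives only about 396 events at month 24 and reaches 420 at month 30.7. Completers then number up to 350 × (30.7 − 23.46)/12 × (0.323 + 0.480), about 68 + 101, and the HR moves from 0.65 to about 0.74.

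**7. CR stops.** The documents give no frequency, timing or arm difference, so every share here is assumed. Equal shares of 5, 10 and 15% per arm (stops spread over months 5.5 to 17.5, completers included) move the whole-arm HR from 0.647 to 0.656, 0.651 to 0.662 and 0.654 to 0.667. With no effect the HR stays at 1.00. Unequal shares, control versus combination:
- 5 vs 6.8%: 0.647 to 0.675
- 15 vs 20.3%: 0.651 to 0.724
- 10 vs 5%: 0.653 to 0.612
- no effect, 5 vs 10%: 0.999 to 1.074
- no effect, 10 vs 5%: 0.999 to 0.928

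**The case against.** Four points can be made against this.

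First, the section defers detail to a supplemental SAP, which may already exempt these stops. That stands as a limit: the protocol text has no exception, but one cannot say that the full plan lacks one.

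Second, the matter may be moot. IA2 has been reviewed, Section 8.1 says only selected analyses will follow, and central imaging review is no longer required (4.2.3.1.1, 7.1.5). Nothing shows that Sensitivity Analysis 2 will be reported. This limits the consequence but does not correct the rule.

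Third, the completion effect is close to nil. Thirteen events is an upper bound for dosing on schedule: late Japanese enrollment (8.1), dose delays and earlier stops all reduce it. The primary analysis and Sensitivity Analysis 1 also stand alongside for comparison. I accept this, and it is why the point is minor.

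Fourth, counting every stop as failure could be deliberate conservatism. This does not hold, because the rule is not reliably conservative: under assumed shares it moves the HR up or down depending on which arm has more CR stops.

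A reader might infer from the unequal-share figures, or from 0.74 at the late cut, that the rule would materially distort this trial's PFS result. The documents do not support that. The CR shares are assumptions, and the late cut needs a whole-arm HR of 0.65, which sits badly with the reported lack of benefit.

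**Conclusion.** The rule as written misclassifies two groups of progression-free subjects as progressed. This follows from setting Section 8.6.1.1 beside Section 5.8.1 and needs no modelling. It touches neither the primary PFS test nor alpha nor power.

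Completion alone at month 24 adds about 0 to 15 events among 700 subjects, with an expected HR shift of 0.01 or less and none on average if there is no true effect. The 0.01 must not be read as a cap on any single trial. The figures assume uniform accrual, no earlier stops and unstratified estimation, whereas the plan stratifies. A cut near month 31 under whole-arm HR 0.65 would give about 0.74. CR stops cannot be sized from the documents: equal stopping by arm shifts the HR by about 0.01 or less (0.013 at the largest share tried), and unequal stopping can move it either way. Severity: minor.

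**What to change.** In the Section 8.6.1.1 narrative and the first row of Table 11, let Sensitivity Analysis 2 count a discontinuation as a PD event only when the reason is something other than completing 35 pembrolizumab administrations or stopping in confirmed CR. Censor those two groups at the last disease assessment, and make the supplemental SAP match.

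If the analysis has already been run, keep the pre-specified version and add the corrected one, labelled post hoc. Replacing a pre-specified analysis after unblinding would not be sound.

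The cost is one sentence, one table cell, a matching supplemental SAP entry and, if already run, one further run. Completers can be identified from cycles received, which Section 8.12 already summarises. The practical difficulty is CR: Section 8.6.3 displays the primary reason for discontinuation but does not say that CR is a separate category, so it must be confirmed that CR stops are identifiable.

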#### **8.6.1.2 Overall Survival (OS)**

To address the primary OS hypothesis, the Kaplan-Meier method will be used to estimate the OS curves. The treatment difference in survival will be assessed by the stratified log-rank test. A stratified Cox proportional hazard model with Efron's method of tie handling will be used to assess the magnitude of the treatment difference (i.e., the hazard ratio). The hazard ratio and its 95% confidence interval from the stratified Cox model with a single treatment covariate will be reported. The same stratification factors used for randomization (see Section 5.4) will be applied to both the stratified log-rank test and the stratified Cox model.

#### **8.6.1.3 Objective Response Rate (ORR)**

To address the secondary ORR hypothesis, stratified Miettinen and Nurminen's method [57] with weighting based on group size will be used for comparison of the objective response rates between the treatment groups. A 95% confidence interval for the difference in response rates between the pembrolizumab + epacadostat regimen and the pembrolizumab + placebo regimen will be provided. Sensitivity analyses will be performed for ORR using Cochran-Mantel-Haenszel test. Associated odds ratios and 95% CIs will be calculated. The same stratification factors used for randomization (see Section 5.4) will be applied to the analysis. [Table 12](#) summarizes the key efficacy analyses.

Table 12 Analysis Strategy for Key Efficacy Variables

Endpoint/Variable (Description, Time Point)	Statistical Method	Analysis Population	Missing Data Approach
Dual Primary Hypotheses #1 and #2			
Progression free-survival (per independent central review as assessed by RECIST 1.1)	Testing: Stratified Log-rank test Estimation: Stratified Cox model with Efron's tie handling method	ITT	Model based
Overall survival	Testing: Stratified Log-rank test Estimation: Stratified Cox model with Efron's tie handling method	ITT	Model based
Secondary Objectives			
ORR (per independent central review as assessed by RECIST 1.1)	Testing and estimation: Stratified Miettinen and Nurminen's method	ITT	Model based
DOR (per independent central review as assessed by RECIST 1.1)	Testing: Stratified Log-rank test Estimation: Stratified Cox model with Model based Efron's tie handling method	ITT (responder subs Model based et)	Model based

The strategy to address multiplicity issues with regard to multiple efficacy endpoints and interim analyses is described in Section 8.7, Interim Analyses and in Section 8.8, Multiplicity.

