#### **3.2 Secondary Objective(s) & Hypothesis(es)**

In all randomized male/female subjects with histologically confirmed diagnosis of melanoma with unresectable or metastatic melanoma of at least 18 years of age:

[figure not shown]
- 1) **Objective:** To compare the objective response rate (ORR) of the 2 treatment groups based on RECIST 1.1 by independent central review.

**Hypothesis (H1):** The combination of pembrolizumab and epacadostat increases ORR based on RECIST 1.1 by independent central review compared to pembrolizumab and placebo.

- 2) **Objective:** To evaluate the safety and tolerability of the 2 treatment groups.
- 3) **Objective:** To evaluate the duration of response (DOR) of the 2 treatment groups based on RECIST 1.1 by independent central review.
- 4) **Objective:** To evaluate the pharmacokinetics (PK) and anti-pembrolizumab antibodies of pembrolizumab and epacadostat administered concomitantly.

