## **8.4 Analysis Endpoints**

Efficacy and safety endpoints that will be evaluated for between-treatment differences are listed below, followed by the descriptions of the derivations of selected endpoints.

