#### **Secondary**

Duration of response (DOR) determined by disease assessment is defined as the time from the earliest date of qualifying response until earliest date of disease progression or death from any cause, whichever comes first based upon blinded independent radiologists' RECIST 1.1 assessment.

Objective response rate (ORR) is defined as the proportion of the subjects in the analysis population who have a confirmed complete response (CR) or partial response (PR) based on RECIST 1.1 by independent central review.

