## **8.6 Statistical Methods**

Statistical testing and inference for efficacy analyses are described in 8.6.1. Efficacy results that will be deemed to be statistically significant after consideration of the Type I error control strategy are described in Section 8.8, Multiplicity. Nominal p-values may be computed for other efficacy analyses, but should be interpreted with caution due to potential issues of multiplicity, sample size, etc. Unless otherwise stated, all statistical tests will be conducted at  $\alpha=0.05$  (2-sided) level.

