## **8.8 Multiplicity**

The multiplicity strategy specified in this section will be applied to the overall ITT population for the testing of primary hypotheses. The overall type I error is strongly controlled at 2.5% (one-sided) for the multiple endpoints tested, as well as for the multiple analyses of overall survival planned using the methods of Maurer and Bretz [59], with 1.25% allocated up front to the PFS hypothesis and 1.25% allocated up front to the OS hypotheses. The trial is considered statistically positive if either PFS or OS is positive.

The superiority of PFS will be tested at 1.25% in this study. If the pembrolizumab + epacadostat combination regimen demonstrates superior PFS, the 0.0125 alpha will be re-assigned to the comparison of OS. Should the OS comparison be statistically significant, the alpha assigned to OS will be reassigned to the comparison of ORR.

A graphical display of the plans for re-allocation of alpha is displayed in [Figure 3](#).

[figure not shown]

Figure 3 Graphical Display of Testing Strategy

For the PFS and OS hypothesis, an exponential alpha-spending function (see Anderson and Clark [60]) with  $\nu=0.75$  (approximating an O'Brien-Fleming boundary) will be used. For PFS the cumulative alpha will be 1.25% unless OS and ORR are statistically significant, in which case the 1.25% alpha associated with OS will be reallocated to PFS and testing will be done at 2.5% alpha. For OS, the cumulative alpha will be 1.25% (if PFS superiority is not demonstrated) or 2.5% (if PFS superiority is demonstrated).

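### Table 12 compares duration of response between arms among responders only, a comparison that randomisation does not protect if epacadostat changes who responds

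*Combined protocol and SAP*

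**What the plan says.** The DOR row of Table 12 (Section 8.6.1.3) reads "Testing: Stratified Log-rank test Estimation: Stratified Cox model with Model based Efron's tie handling method", with the analysis population given as ITT restricted to responders. The stray words in that row come from reading the PDF and are not part of the complaint.

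The between-arm comparison is intended. Section 8.4 opens with "Efficacy and safety endpoints that will be evaluated for between-treatment differences are listed below", and DOR is one of the secondary endpoints that follow: "Duration of response (DOR) determined by disease assessment is defined as the time from the earliest date of qualifying response". The clock therefore starts at response.

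The objective in Section 3.2 is more modest: "To evaluate the duration of response (DOR) of the 2 treatment groups based on RECIST 1.1 by independent central review". No DOR hypothesis is stated. Section 8.8 passes alpha among PFS, OS and ORR only ("Should the OS comparison be statistically significant, the alpha assigned to OS will be reassigned to the comparison of ORR"), so DOR receives none. Section 8.6 allows nominal p-values for other efficacy analyses, which "should be interpreted with caution due to potential issues of multiplicity, sample size, etc", and sets a two-sided 0.05 level as the default for tests.

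On response itself, Section 3.2 hypothesises that the combination increases ORR. Section 8.9.1 takes 35% on control and states that "the study has ~97% power to detect an ORR rate for the combination regimen of 50" per cent.

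**The concern.** A log-rank test or hazard ratio estimates a treatment effect when the compared groups were formed by randomisation. Here they are formed by response, which comes later and which the plan itself expects treatment to change. If epacadostat turns some non-responders into responders, the combination's responder group contains patients with no counterpart among control responders. They may hold their responses for a shorter or a longer time than the rest. A difference in DOR can then appear although no patient who would have responded on either arm has a changed duration.

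Stratifying by PD-L1 and BRAF balances only those two factors. The visible caution in Section 8.6 concerns multiplicity and sample size, does not mention selection on response, and applies to p-values but not to the hazard ratio. What is at stake is the reading of the clinical study report: a DOR hazard ratio and p-value could be taken as evidence about durability when they also reflect who became a responder.

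**Working it through.** **1. The plan's own response assumption.** Inputs: ORR 35% vs 50%, one-sided alpha 2.5% (Section 8.9.1), 1:1 allocation.

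Power = Φ{[0.15 − 1.96·√(2·0.425·0.575/n)] / √[(0.35·0.65 + 0.50·0.50)/n]}, with n per arm.

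- n = 300: Φ{(0.15 − 0.0791)/0.0399} = 96.2%
- n = 350: Φ{(0.15 − 0.0732)/0.0369} = 98.1%

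These bracket the stated ~97%, so the plan does rest on a treatment effect on response. It states no event count or power for DOR.

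**2. How different the responder groups would be.** With about 700 patients (Section 8.1), 350 per arm: control 0.35 × 350 ≈ 122 responders; combination 0.50 × 350 = 175. If every control responder would also respond on the combination (an assumption), about 53 of the 175, or 30%, have no control counterpart.

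**3. What that does to the hazard ratio.** The following are assumptions, because the documents give no DOR distribution:

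- exponential DOR with no plateau;
- a 24-month median for the shared responders in both arms, so no true effect on their durability;
- a median of m months for the extra responders.

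At the start of follow-up the hazard ratio is (122 + 53 × 24/m)/175:

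- m = 8: 281/175 = 1.61
- m = 12: 228/175 = 1.30
- m = 16: 201.5/175 = 1.15
- m = 24: 175/175 = 1.00
- m = 36: 157.3/175 = 0.90

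As the shorter-lived responses end, the mixture moves back towards the shared group, so the average ratio over follow-up is nearer 1.

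**4. Simulation over realistic follow-up.** Follow-up after response is 9 to 21 months: IA2 at about 24 months (Section 8.7.1), less 0 to 12 months of enrolment (Section 8.9.1), less about 3 months to response. The last figure is an assumption. It is suggested by the Week 12 imaging start in Section 7.1.8.4.2, which describes follow-up imaging and no longer applies. There were 4,000 trials per scenario, with a stratified log-rank test at |z| > 1.96 and a stratified Cox hazard ratio. Six strata had assumed, non-prognostic shares. The Monte Carlo standard error is at most 0.8 points.

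| ORR | Quantity | m = 8 | 12 | 16 | 24 | 36 |
|---|---|---|---|---|---|---|
| 35% vs 50% | HR | 1.47 | 1.27 | 1.14 | 1.00 | 0.90 |
| | significant against combination | 52% | 21% | 8% | 2% | 1% |
| | significant in favour | 0% | 0% | 0% | 3% | 7% |
| 35% vs 45% | HR | 1.33 | 1.20 | 1.11 | 1.00 | 0.93 |
| | significant against combination | 29% | 13% | 7% | 2% | 1% |
| 35% vs 40% | HR | 1.18 | 1.11 | 1.06 | 1.00 | 0.96 |
| | significant against combination | 12% | 8% | 4% | 3% | 1% |

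Significance in favour reaches at most 6% at 35% vs 45% and 3% at 35% vs 40%. With no drug effect (35% vs 35%, same DOR) the HR is 1.00, with 2.4% against and 2.3% in favour, which is nominal. An unstratified run moved the hazard ratios by at most 0.01 and the rejection rates by about 2 points.

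**5. A second set of assumptions.** With uniform censoring from 6 to 22 months, unstratified tests and m from 6 to 72 months, 35% vs 50% gave hazard ratios from 1.60 (69% of trials significant against) to 0.78 (21% significant in favour). The bias again ran in both directions.

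**The case against.** The strongest reply is that the plan claims little for DOR. It has no hypothesis, no alpha and no stated causal target, and Table 12 openly says the analysis is in responders. As a contrast between observed responders, the hazard ratio is what it says it is. The caution in Section 8.6 ends in an open list, and part of Section 8.6.1 is redacted, so absence can be asserted only for the visible text. This limits the importance of the point. It does not make the comparison randomised, and nothing visible tells the reader that it is not.

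The second reply is that little remains to be affected. Section 2.1 reports that "An interim review of the data indicated no benefit of epacadostat over placebo when combined with pembrolizumab", and Section 8.1 says only selected analyses will follow. DOR is neither named nor dropped there. If the drug has no effect at all, the test is valid. This stands, although the statement in Section 2.1 does not report ORR, so equal response is plausible but not shown.

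The third reply is that the sizes depend on the inputs. With m = 12 and 35% vs 50%, changing the shared-responder median from 24 months to 12, 36 or 48 changes rejections against the combination from 21% to 2%, 44% or 62%. Section 8.9.1 also assumes a 30% plateau in PFS. If those patients are mostly responders, about 30/35 = 86% of control responders have a plateau. With the same plateau in both responder types, rejections are nominal; with 95% in the extra responders, the hazard ratio is about 0.79. But with 50% or 70% in the extra responders, it is 1.76 or 1.36, with 44% or 14% of trials significant against. So the magnitude is uncertain and the bias remains.

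Finally, Kaplan-Meier curves by arm carry the same selection. That is true. Dropping the p-value and hazard ratio removes the formal inference, not the need for care in reading the curves.

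**Conclusion.** The concern holds, at minor importance. Table 12 prescribes an inferential between-arm comparison in a subset defined by an outcome that the plan expects treatment to change. Whenever treatment changes response, randomisation no longer protects that comparison, and it may be biased in either direction.

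That conclusion does not depend on the simulations; the size does. The bias was large only with a wide ORR gap and extra responses clearly shorter-lived than the rest, under an assumed exponential DOR and an assumed 24-month shared median. No figure here should be cited as the bias in this trial. The PFS, OS and ORR tests and the overall type I error are unaffected, and DOR cannot make the trial positive.

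**What to change.** In the DOR row of Table 12, replace the log-rank test and Cox model with Kaplan-Meier estimates by treatment group among responders: median, range, and the proportion still in response at fixed times. State that no between-group p-value or hazard ratio will be given. Add one sentence to Section 8.4 saying that DOR is summarised by arm among responders and is not compared between arms. This still meets the Section 3.2 objective, which is to evaluate DOR.

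The trial is already unblinded, so record this as a dated post-unblinding change. If the comparison has already been run, keep it in the clinical study report, label it descriptive and non-randomised, and draw no conclusion about durability from it.

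The cost is one table row and one sentence, or one label in the report. The downside is that the trial will have no inferential DOR comparison, and the removal of a pre-specified analysis must be disclosed.
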